4.6.3 Pharmacokinetic Analyses

The analysis of PK variables will be conducted by Clinical Pharmacology and reported in the CSR.

4.6.4 Immunogenicity Analyses

The analyses will be carried out on the immunogenicity analysis population

The numbers and proportions of ADA-positive participants and ADA-negative participants at baseline (baseline prevalence) and after study drug administration (post-baseline incidence during both the treatment and follow-up periods) will be summarized.

 Participants are considered to be ADA positive if they are ADA negative at baseline but develop an ADA response following study drug administration (treatment-induced ADA response), or if they are ADA positive at baseline and the titer of one or more post-baseline samples is greater than the titer of the baseline sample by a scientifically reasonable margin such as at least 4-fold (treatment-enhanced ADA response).

 Participants are considered to be ADA negative if they are ADA negative at baseline and all post-baseline samples are negative, or if they are ADA positive at baseline but do not have any post-baseline samples with a titer that is greater than the titer of the baseline sample by a scientifically reasonable margin such as at least 4-fold (treatment unaffected).

4.7 INTERIM ANALYSES

4.7.1 Planned Interim Analyses

There will be up to four planned interim analyses for each treatment arm. The exact number of planned interim analyses will depend on the overall duration of the treatment arm as well as the sequencing of the drugs in the treatment arm.

The first three interim analyses will occur, depending on the overall duration of the treatment arm as well as the sequencing of the drugs in the treatment arm, once all participants within a treatment arm have been randomized and have reached 12, 24, and EOT respectively after the start of therapy (or have discontinued from the study). The fourth interim analysis will be performed when all participants within a treatment arm have completed the follow-up Week 12 visit (or have discontinued the study).

Additional design considerations are provided. The below timing of planned interim analyses and RGT are illustrated based on a 48-week treatment duration arm; for arms with shorter treatment duration, the number of the interim analyses as well as the RGT early treatment discontinuations will be adjusted accordingly.

- First interim analysis at 12 weeks for a treatment arm: if the observed ontreatment HBsAg loss rate of a combination is at least 30% greater than that of control, the Sponsor will take into consideration the available safety and pharmacodynamics data and may commence a new treatment arm of sample size of approximately 30 participants with 12-weeks' treatment duration.
- Second interim analysis at 24 weeks for a treatment arm: if the observed-on treatment HBsAg loss rate of a combination is at least 30% greater than that of control, the Sponsor will take into consideration the available safety and pharmacodynamics data and may commence a new treatment arm of sample size of approximately 30 participants with 24-weeks treatment duration.
- Third and fourth interim analyses at Week 48 and follow-up Week 12: for safety and internal decision-making purposes (e.g., front-loading Ph3 activities), and if the observed HBsAg loss rate of a combination is at least 30% greater than that of control, the Sponsor may decide to expand the treatment arm up to approximately 100 participants. An expansion may also be triggered prior to EOT, for a treatment arm that gives an early indication of efficacy. The decision criteria to trigger an expansion arm in this case, will be documented as an appendix to the IMC/SOC charter.

Above pre-specified study adaptations allow for NME combination therapies that show promising efficacy outcomes to be further evaluated promptly, based on emerging data, without delays that would be otherwise incurred through protocol amendments. These decision criteria assume that the on-treatment HBsAg loss rate is predictive of the 24-week post-EOT HBsAg loss rate.

Given the hypothesis-generating nature of this study, the Sponsor may choose to conduct additional interim analyses not specified above. The decision to conduct an optional interim analysis and the timing of the analysis will be documented in the Sponsor's trial master file prior to the conduct of the interim analysis. The interim analysis will be performed and interpreted by Sponsor study team personnel

The following endpoint will be assessed as part of the interim analysis:

Efficacy endpoint:

- HBsAg loss
- 2) Change in HBsAg and anti-HBs over time
- 3) HBsAg seroconversion (loss of HBsAg and presence of anti-HBs antibody)
- 4) Changes in HBeAg and anti-HBe status
- HBeAg loss and seroconversion
- 6) HBC DNA

Safety Endpoint:

- All clinical adverse events (AEs)
- Serious Adverse events
- 3) Adverse events of special interest (AESI)
- 4) Liver/ Renal/ Urine Analysis Function Test and some important Lab parameters
- Laboratory abnormalities

The estimated treatment difference adjusted for baseline HBsAg level, along with the associated 95% confidence interval in the proportion of participants with HBsAg loss for each interim analysis between the experimental and associated control arm will be provided.

Confidence interval will be estimated using Cochran-Mantel-Haenszel (CMH) weighting method with continuity correction. Participants with missing or no response assessments will be classified as non-responders.

Summary descriptive statistics will be used to summarize these efficacy and safety outcome measures at each of the time points by treatment group. In addition, graphical displays will be produced of mean and individual participant data as appropriate. Means and change from baseline for efficacy and safety endpoints will be provided. Mean (95% Cis) and individual HBsAg maximum decrease from baseline will be provided. ALT increase plots will be provided.

5. SUPPORTING DOCUMENTATION

5.1 APPENDIX 1 ANALYSIS DETAILS SPECIFIC TO NUC CONTROL ARM

An overview of the nucleos(t)ide (NUC) control treatment arm is shown in appendix 7 in protocol.

Participants will continue their background NUC therapy for the 48-week treatment period. At the end of the treatment period, in line with current CHB treatment guidelines, participants will continue NUC treatment during the follow-up unless the NUC discontinuation criteria have been met.

Initially, 30 participants will be randomized to the NUC control arm. The subsequent randomization ratio will depend on the number of actively enrolling NME treatment arms, with the stipulation that no more than 17% of participants will be randomly allocated to the NUC control arm.

The NUC control arm is a continuous recruiting arm and the number of patients in this arm will depend on new enrolling NME. For any major reporting event, the number patients who completed study will be included in the corresponding reporting event.

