4.4 END-OF-STUDY DEFINITION

A participant is considered to have completed the study if he/she has completed all phases of the study including the last study visit. The end-of-study is defined as the date when the last participant completes the last visit (LPLV).

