The timing of planned interim analyses and RGT below are illustrated based on a 48week treatment duration arm; for arms with shorter treatment duration, the number of the interim analyses as well as the RGT early treatment discontinuations will be adjusted accordingly.

Analysis	Timing of Analysis
First interim analysis	All participants in the study have completed their 12-week visit for a treatment arm or discontinued prematurely
Second interim analysis	All participants in the study have completed their 24-week visit for a treatment arm or discontinued prematurely
Third interim analysis	All participants in the study have completed their 48-week (EOT) visit for a treatment arm or discontinued prematurely
Fourth interim analysis	All participants in the study have completed their follow-up week 12 visit or discontinued prematurely
Primary	All participants in the study have completed their follow-up week 24 visit or discontinued prematurely
Final	The end-of-study for a treatment arm is defined as the date when the last participant completes their follow-up week 48 visit or discontinued prematurely

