3. ANALYSIS SETS

The participant analysis sets for the purposes of analyses are defined in Table 3.

Table 3 Participant Analysis Sets

Population	Description
Safety	All participants randomized to a treatment regimen who received at least one dose of any drug for their assigned treatment regimen, whether prematurely withdrawn from the study or not, will be included in the safety analysis.
Modified ITT	All participants who were randomized and received at least one dose of each drug for their assigned treatment regimen. Participants will be analyzed according to the treatment arm to which they were randomized.

Pharmacokinetic	Participants will be excluded from the PK analysis population if they significantly violate the inclusion or exclusion criteria, deviate significantly from the protocol, or if data are unavailable or incomplete which may influence the PK analysis. Excluded cases will be documented together with the reason for exclusion. All decisions on exclusions from the analysis will be made prior to database closure.
Immunogenicity	All Participants who had at least one pre- dose (baseline) or at least one post-dose ADA assessment will be included and analyzed according to the treatment they actually received or were allocated to receive,

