4.1 GENERAL CONSIDERATIONS

Disposition and protocol deviations listings and summaries will be based on all randomized participants. Analysis of safety will be based on the safety population. Pharmacodynamics and efficacy analysis will be based on the modified intention-to-treat (mITT) population. Pharmacokinetic analysis will be based on PK population. Immunogenicity analysis is based on the immunogenicity population.

For the treatment arms where additional patients have been recruited to proactively mitigate any impact of COVID-19 or force majeure events, the primary analysis will be performed when approximately 30 patients considered evaluable for the primary analysis reach the primary endpoint of Week 24 post EOT. If the primary analysis is positive for an experimental treatment arm, any additional patients that have been recruited to that treatment arm, will continue and be included in the final CSR.

Evaluable patients: A patient from the mITT population will be considered 'evaluable' if no more than two consecutive siRNA missing doses due to non-safety reasons (e.g., COVID-19 disruptions). This is based on the siRNA liver half-life of ~10 weeks.

estimated from ph1 data. Therefore, after two consecutive missing doses the drug left in the liver is expected to be \sim 40%, which was considered adequate as patients would restart dosing so up to 2 missing doses are not expected to have a major impact on the efficacy.

Evaluable patients in mITT population will be used to estimate the primary endpoint/estimand.

Any subject who does not have a virology parameter evaluation during the pre-specified window for 24-week Follow-up visit (either due to missing assessment or due to early withdrawal from the study or study treatment) will be considered as a non-responder. However, if the subject with missing evaluation is a responder both before and after the visit window, then the subject will be categorized as a responder for that visit.

Key definitions:

The following definitions will be used:

Baseline: The baseline value is defined as the last available valid (quantifiable continuous or categorical value), non-missing observation for each participant prior to first study drug administration. Repeat and unscheduled assessments will be included in the derivation of the baseline values.

HBsAq Loss: HBsAg loss refers to a negative/undetectable HBsAg level, HBsAg loss is defined HBsAg levels <0.05 IU/mL.

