4.2 PRIMARY ENDPOINTS/ESTIMANDS ANALYSES

4.2.1 Definition of Primary Endpoint(s)/Estimand(s)

Definition of Primary Endpoint:

The primary endpoint is HBsAg loss (qHBsAg <0.05 IU/mL) at week 24 post EOT.

The primary endpoint is calculated for each treatment arm as:

% participants with HBsAg loss= (Number of participants with HBsAg loss / total number of participants) *100

The percentage of participants with HBsAg loss will analyzed using evaluable patients from the mITT population.

Definition of Primary Estimand:

In line with the Estimands addendum to ICH E9, the primary efficacy estimand is defined as follows-

The difference between proportions of HBsAg loss (qHBsAg <0.05 IU/mL) at week 24 follow-up in virologically suppressed adult CHB participants on established NUC therapy, with preserved liver function and without significant fibrosis/cirrhosis, treated with

^{**} Evaluate numerical and longitudinal data to understand the discrepancy.

^{***} Depending on numerical values, these may be rare cases of double positive (HBsAg and anti-HBs) usually seen from baseline. Seroconversion will need to be interpreted using longitudinal data.

combination therapy* versus NUC, irrespective of adherence to IMP or whether prohibited medication and/or food has been taken.

*treatment and dose levels will vary depending on the combination arm and are specified in the relevant arm specific appendix.

The primary efficacy estimand is described by the following five attributes:

- a) **Population**: Evaluable patients from the mITT population as defined in section 3. These will be CHB adult participants who are virologically suppressed for more than 6 months on established NUC therapy as defined by the inclusion and exclusion criteria listed in Protocol WV41073 section 5.
- **b) Primary Endpoint**: % participants with HBsAg loss (qHBsAg <0.05 IU/ml) at 24 weeks post-EOT.
- c) Population level summary: The difference between proportions of HBsAg loss (qHBsAg <0.05 IU/mL) between NME combination over the control arm at week 24 post-EOT
- **d)** Treatment conditions: Treatment and dose levels will vary depending on combination arms and are specified in the relevant arm specific appendix.
- e) Intercurrent Event (ICE):

Table 5 Intercurrent Events Impacting Primary Analyses:

Intercurrent Events	SDR/ NSDR	Estimand Approach
Participants with dose interruptions or switching dose/frequency	SDR	Treatment Policy

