4.6 OTHER ANALYSES

4.6.1 Summaries of Conduct of Study

The number of participants who were randomized, discontinued treatment, completed treatment, discontinued study and completed the study (including follow-up period) will be summarized by treatment. Major protocol deviations will be summarized and listed by each treatment arm. Separate listing will be provided for the patients who have met the NUC discontinuation criteria at EOT or follow-up but have not stopped NUC (reluctant to do).

For each participant assessment, the baseline value will be the latest non-missing assessment prior to the first dose administration, this being study Day 1 pre-dose. In the absence of data on study Day 1, the latest non-missing value collected during screening will be used, if such data are not available then the assessment baseline value will be missing for that participant.

4.6.2 Summaries of Treatment Group Comparability/Demographics and Baseline Characteristics

Descriptive statistics will be generated for demographic and baseline disease characteristics including sex, race, ethnicity, origin (for Asian participants only), age, weight, height, body mass index, HBV DNA and HBsAg levels, and HBV history including but not limited to duration of HBV disease, likely route of transmission, HBV genotype, HBeAg status, previous HBV treatments (including incidence of Peg-IFN), and length of time on NUCs.

For NUC treatment duration calculation, if there is a break of treatment of less than 6 months then the duration will be cumulative, if break of treatment is more than 6 months, then the last continuous course of treatment with any nucleos(t)ide products prior to baseline (categorized as <3 years, >=3 to <5 years, >=5 years to <10 years, and >=10 years) will be counted. The effect of this duration covariate will be examined with respect to efficacy, immunogenicity, and antiviral endpoints in separate analyses.

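### SAP 5.1 admits only NUC controls who completed the study to each report, which conflicts with the mITT set and the non-responder rules; the effect is small but the sentence should be replaced

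*SAP*

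**What the plan says.** SAP 5.1 (Appendix 1, NUC control arm) notes that the control arm keeps recruiting as new combinations open. It then gives the only sentence in the SAP on which controls enter a given report: "For any major reporting event, the number patients who completed study will be included in the corresponding reporting event".

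The documents give completion a meaning. Protocol 4.4: "A participant is considered to have completed the study if he/she has completed all phases of the study including the last study visit". SAP 4.6.1 treats leaving early and completing as separate disposition categories: "discontinued study and completed the study (including follow-up period) will be summarized by treatment". A control has 48 weeks of treatment and 48 weeks of follow-up (Protocol 4.1 and Appendix 7).

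The general analysis rules are different:

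- SAP 3, modified ITT: "All participants who were randomized and received at least one dose of each drug for their assigned treatment regimen".
- SAP 4.2.1, primary endpoint: "The percentage of participants with HBsAg loss will analyzed using evaluable patients from the mITT population". SAP 4.1 defines evaluability by missed siRNA doses, so it removes no NUC control.
- SAP 4.1, no virology result in the follow-up Week 24 window: a gap "due to early withdrawal from the study or study treatment) will be considered as a non-responder", unless the participant responded both before and after the window.
- SAP 4.7.1 also counts missing assessments as non-response at the interim analyses.

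On timing, SAP Table 2 sets the primary analysis at "All participants in the study have completed their follow-up week 24 visit or discontinued prematurely". SAP 4.7.1 sets the first three interims when participants "have reached 12, 24, and EOT respectively after the start of therapy (or have discontinued from the study").

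**The concern.** The control group enters every primary and interim difference. If SAP 5.1 is programmed as worded, a control who leaves the study early drops out of the denominator, while an experimental participant who does the same stays in as a non-responder. The two groups being compared are then built by different rules. Controls with a usable follow-up Week 24 result can also be left out of the primary analysis because their last visit is still to come.

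A programmer could build three different control groups from the present text: all mITT controls, controls who have reached the reported visit, or Week 96 completers. In an open-label trial that choice should be settled before results are seen.

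**Working it through.** **1. What the sentence excludes.** Control completion = 48 + 48 = Week 96. Follow-up Week 24 for a control = 48 + 24 = Week 72. At the primary analysis, a control between Week 72 and Week 96 (a span of 96 − 72 = 24 weeks) has the endpoint but has not completed. For a 48-week arm, the corresponding spans at the four interims are:

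- Week 12: 96 − 12 = 84 weeks
- Week 24: 96 − 24 = 72 weeks
- Week 48: 96 − 48 = 48 weeks
- follow-up Week 12: 96 − 60 = 36 weeks

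At the final analysis the span is 0. These are calendar spans, not participant counts. The number affected cannot be computed because the documents give neither accrual nor control drop-out.

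**2. The rules side by side.** Take a control who withdraws from the study before follow-up Week 24. Under SAP 3, 4.1 and 4.2.1 this participant is in the denominator as a non-responder. Under SAP 5.1 the participant is not in the report. No section says which rule prevails.

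**3. The plan's own power figure.** Inputs from SAP 2.2: 3% against 33%, 30 per arm, two-sided 5%, continuity-corrected chi-squared test. With pooled rate p̄:

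- power = Φ[(d − cc − 1.96·se0)/se1]
- cc = 0.5(1/n1 + 1/n2)
- se0 = √[p̄(1 − p̄)(1/n1 + 1/n2)]
- se1 = √[p1(1 − p1)/n1 + p2(1 − p2)/n2]

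At 30 and 30: p̄ = 0.18, cc = 0.0333, se0 = 0.0992, se1 = 0.0913. The bracket is (0.300 − 0.0333 − 0.1944)/0.0913 = 0.79, giving 78.6% against the stated 78%. Keeping the experimental arm at 30 and cutting controls to 27 or 24 gives 74.9% or 70.2%. No formal test is planned, so this only gauges lost precision.

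**4. Effect on the control rate.** Assumptions: one control responder, who completes; 10% or 20% of controls leave before the reported visit and would otherwise count as non-responders.

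| Controls before exclusion | All kept | 10% dropped | 20% dropped |
|---|---|---|---|
| 30 | 1/30 = 3.3% | 1/27 = 3.7% | 1/24 = 4.2% |
| 40 (assumed larger pool) | 1/40 = 2.5% | 1/36 = 2.8% | 1/32 = 3.1% |

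The shifts are 0.37 and 0.83 points for the first row, and 0.28 and 0.62 for the second.

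**5. Effect on the difference.** Assume 10/30 experimental responders. The Newcombe 95% limits combine the Wilson limits (l, u) of each rate: lower = d − √[(p1 − l1)² + (u2 − p2)²], upper = d + √[(u1 − p1)² + (p2 − l2)²]. They are unstratified, so they are not the SAP's CMH interval.

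| Control | Difference | 95% CI |
|---|---|---|
| 1/30 | 30.0% | 10.6 to 48.1 |
| 1/24 | 29.2% | 7.8 to 47.4 |
| 1/40 | 30.8% | 13.3 to 48.8 |
| 1/32 | 30.2% | 11.3 to 48.3 |
| 0/30 | 33.3% | 15.2 to 51.2 |
| 0/24 | 33.3% | 13.6 to 51.2 |

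With no control responders the difference does not move and only the lower limit falls. At the SAP's 3% rate, the chance of no responder among 30 controls is 0.97³⁰ = 40%.

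**6. The 30-point criterion in SAP 4.7.1.** With one responder among 30 controls, 10/30 experimental responders meet it exactly (33.3 − 3.3 = 30.0). With 27 or 24 controls the differences are 29.6 and 29.2, so 11/30 are needed. With no control responder the requirement stays at 9/30. With a pool of 40 cut to 36 or 32, 10/30 still meets it (33.3 − 2.8 = 30.6; 33.3 − 3.1 = 30.2).

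**The case against.** The best defence is that the sentence is a loosely worded data cut. It follows directly on the remark that the control arm recruits continuously, and it does not claim to override the analysis sets or the missing-data rules. NUC control is one of the listed treatment arms, so the general rules should apply to it. Protocol 9 says an arm's complete data are analysed once everyone has finished follow-up or discontinued early, which makes it plausible that completion is shorthand for mature data. This stands as an account of intent. It does not cure the text: 5.1 does not say so, and a rule based on reaching the reported visit by completing it still omits controls who left before it.

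A reader might infer more than the documents support, in four ways:

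- **That the timing text is also contradicted.** It is not. Table 2 and SAP 4.7.1 say when an analysis runs, not who is in it. They are context only.
- **That no control randomised alongside an arm could have completed by an interim.** Accrual is not given. At the fourth interim the last participant is at Week 60, so a control randomised 36 weeks earlier could be at Week 96.
- **That the rule flatters the experimental arm.** Dropping controls who would have counted as non-responders raises the control rate or leaves it at zero. For controls excluded only because they have not reached Week 96, the direction cannot be predicted.
- **That expansion decisions would be overturned.** The change from 10/30 to 11/30 in step 6 depends on one control responder and a pool of 30. The criterion only permits the sponsor to act.

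**Conclusion.** The sentence in SAP 5.1 is wrong as written. With completion defined as it is, the rule excludes early leavers from the control arm and, at the primary analysis, excludes controls who already have the endpoint. Both exclusions conflict with the mITT efficacy set and the non-responder rules, and nothing in the documents reconciles them. Under the charitable reading the first exclusion remains, in the control arm only.

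The consequence is modest: about 0.3 to 0.8 points on the control rate, against the experimental arm, some loss of precision, and no change in the point difference when there are no control responders. These figures rest on assumed drop-out of 10 to 20%, one control responder who completes, and a pool of 30 or 40. Protocol 1.2 allows the pool to exceed 30. Estimates and intervals are affected, not a test decision, because no formal test is planned. The sentence should be corrected before the next reporting event, but it does not threaten the trial's conclusions.

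**What to change.** Replace the sentence in SAP 5.1 with:

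> At each reporting event the control group is all NUC-control mITT participants whose scheduled visit for the reported time point, including the standard visit window (and any extension granted to that participant), falls on or before the data cut-off, whether or not they discontinued; missing data follow the same non-responder rules as the experimental arm. For post-treatment time points the control visit is the one the same number of weeks after the control's own EOT (Week 48), unless the arm-specific appendix states otherwise.

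The window wording is needed because the control schedule in Protocol Appendix 7 allows ±7 days at follow-up Week 24, extendable to +6 weeks in extreme circumstances. The last sentence is needed because the PD-L1 LNA arms end treatment at Week 24 or Week 36 while controls end at Week 48.

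This keeps the data cut that a continuously recruiting control arm requires. It costs an edit to one SAP paragraph and needs no new data, tables or participants.
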